5.7. Measurements

5.7.1. Outcome variables

Efficacy analyses Outcome variables The primary outcome variable will be the number of days drinking (prior 3 weeks, TLFB) at 6 and 9 months. We chose this variable because (a) days drinking was the main outcome in the HWHL trial,¹⁶ (b) of several self-reported drinking variables, the number of drinking days was most highly correlated (Spearman $r=0.74$) with PEth level in a validation study in Uganda,⁹⁵ and (c) this variable may also be the least susceptible to bias because it does not require reporting the number of drinks, which can be challenging where non-standard drinks are common.⁹ We will use PEth level as an objective measure of prior 21-day alcohol use to confirm the findings obtained using self-report. Another main outcome variable will be HIV viral suppression at 9 months. Secondary outcomes will include the AUDIT-C score, which was associated with increased mortality in HIV-infected drinkers,¹³ and the number of heavy drinking days ($\geq 4/5$ drinks per occasion by females/males, respectively), the standard measure for pharmacotherapy trials. Other exploratory outcomes will include CD4 cell count and ART adherence.

Booster uptake and satisfaction Outcome variables Tech booster uptake will be measured from data extracted from the technology databases that record the SMS and IVR interactions. Uptake will be the proportion of sessions in which the participant answered all the questions prior to the final sign-off message; the denominator for this will be the number of tech booster sessions initiated by the system. Live booster call uptake will be tabulated from the counselor's call record forms that will be entered weekly into the study database. We will also determine the proportion of participants who request a counselor call back. We will also calculate intervention satisfaction in each arm using the Client Satisfaction Scale-8.¹⁴⁵ Among those in the tech booster arm (Arm 2), we will calculate usability via the System Usability Scale, used to evaluate new technology,^{146,147} and the proportions that chose SMS over IVR, overall and by reading literacy (yes/no).

Independent variables The predictor variable will be study arm by month (6 or 9 months).

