5.9.1. Primary analyses

Efficacy analyses

The analysis for primary outcome variable 1 (alcohol reduction) will measure the number of drinking days (of the prior 21) at six months and nine months, in pairwise comparisons of the study arms, controlling for baseline days drinking (of the prior 21).¹⁴⁹ The analyses will be conducted as intention-to-treat, and we will use Poisson or negative binomial regression for the count data, i.e. the number of drinking days at 6 and 9 months, controlling for baseline days drinking. The PEth level will be transformed to log10 PEth before analyses, based on PEth's highly skewed distribution and we will use linear regression for this outcome.

The analysis for primary outcome variable 2 (HIV viral suppression) will use logistic regression to compare the proportions with viral load<500 copies/ml, controlling for baseline viral load. We will adjust these analyses for baseline characteristics that exhibit imbalance between groups (based on a p-value ≤ 0.1 in comparisons of potential confounders listed in Table 3).

Secondary outcomes: Other exploratory outcomes will include CD4 cell count and ART adherence.

Missing data We will evaluate differences in baseline characteristics between those lost to follow-up versus those who are retained.¹⁵² If it is reasonable to assume that data are missing at random, multiple imputation methods will be applied to account for the missing data.^{152,153} We will also consider pattern mixture models,¹⁵⁴ which are applicable when the data are missing not at random.

Statistical power: With a sample size of 90 in each arm, assuming 90% 9-month retention, using a simplifying t-test for power calculations, we will have 80% power to detect a difference in the number of drinking days in the prior 21 between two study arms at nine months of ≥ 2.4 days, i.e. nearly 1 fewer day per week, as statistically significant ($\alpha=0.05$) assuming that the mean number of drinking days in the prior 21 in the control group is 7 (standard deviation is 5.5, based on prior data). Given that this is a pilot study we will not adjust for multiple comparisons.

Booster uptake and satisfaction analyses

Analyses We will calculate 95% confidence intervals for the outcomes listed above. We will conduct preliminary tests of whether the mean completion proportions and satisfaction scores differ by booster arm (live versus tech) by conducting 2-sample tests (t-test or Mann-Whitney).

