5.9.2. Additional analyses

Exploratory analyses will examine the exposure to the boosters, in an as-treated analysis. For example, within the tech arm, we may examine whether the number of completed booster sessions is associated with the number drinking days in the prior 21, at six and nine months. Because these are non-randomized exposures, we will explore using propensity score analyses¹⁵⁰ to attempt to balance the groups. We will also examine effect moderation by variables found to impact intervention efficacy, such as gender and depression¹⁵¹ and by literacy.

PEth versus self-report We will consider findings that are concordant by self-report and PEth (i.e. both analyses statistically significant or both not reaching statistical significance) to be conclusive. If the findings are discordant, we will examine the pattern of SDS scores and demand characteristics (Table 3). We found in our previous studies that, after controlling for PEth level, adjusted SDS means were 0.88 points lower ($p<0.01$) for those reporting versus those denying recent unhealthy alcohol use, while PEth levels were not associated with SDS ($p=0.28$, unpublished analyses). We will conclude in favor of the PEth results if the patterns are consistent with under-report (i.e. associations of higher SDS and demand scores with lower self-reported alcohol use at the same PEth level, suggesting under-reporting).

Missing data We will evaluate differences in baseline characteristics between those lost to follow-up versus those who are retained.¹⁵² If it is reasonable to assume that data are missing at random, multiple imputation methods will be applied to account for the missing data.^{152,153} We will also consider pattern mixture models,¹⁵⁴ which are applicable when the data are missing not at random.

6. Safety considerations

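### Agreement between self-report and PEth is judged by matching significance verdicts, which split by chance in about one comparison in six at the design effect and do not show whether the two effects differ

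*Combined protocol and SAP*

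**What the plan says.** The primary efficacy outcome is drinking days in the prior 21, by self-report, at six and nine months. PEth is there to confirm it (section 5.7.1) and is analysed by linear regression on the log10 scale (section 5.9.1). Section 5.7.1 supports the pairing with a Ugandan validation study in which, among the self-report measures, "the number of drinking days was most highly correlated" with PEth, at a Spearman coefficient of 0.74.

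Section 5.9.2 gives the rule for reading the two together. Findings are concordant when they are "both analyses statistically significant or both not reaching statistical significance". For the rest: "If the findings are discordant, we will examine the pattern of SDS scores and demand characteristics". PEth then prevails if, at a given PEth level, higher social-desirability and demand scores go with lower reported drinking.

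Each comparison is judged at 0.05: "Given that this is a pilot study we will not adjust for multiple comparisons". Power is stated for self-report only: "we will have 80% power to detect a difference in the number of drinking days in the prior 21 between two study arms". The size of that difference is 2.4 days, and it refers to the nine-month visit. No effect size, SD or power is given for PEth, and no direct comparison of the two effects is planned.

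**The concern.** The rule compares significance labels, not effects. Suppose self-report gives p=0.04 and PEth p=0.06. The rule calls this discordant. The corresponding z-values are 2.05 and 1.88, a difference of 0.17. If the two statistics correlate at 0.74, the standard error of that difference is √(2×(1−0.74)) = 0.72. The gap is then 0.17/0.72 = 0.24 standard errors, which is no evidence of disagreement. By the same logic, two results on the same side of 0.05 may differ in size.

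The harmful case is a true intervention effect that shows on self-report, narrowly misses on PEth, and is then attributed to under-reporting. The trial exists to supply effect sizes for a larger trial, so a misreading here would carry into that design.

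**Working it through.** **Inputs.** From section 5.9.1: 90 per arm, 90% retention (90×0.90 = 81 analysed), SD 5.5, control mean 7, difference 2.4 days, alpha 0.05. The plan does not state sidedness; I take two-sided. From section 5.7.1: correlation 0.74. From section 3: correlations of 0.6-0.8 between PEth and consumption, and reductions of 15-30% in earlier interventions, which on a mean of 7 is 1.05-2.1 days.

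**1. The plan's own figure.** SE = 5.5×√(2/81) = 0.864. Power = Φ(2.4/0.864 − 1.96) = Φ(0.817) = 79.3%. The stated 80% reproduces.

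**2. Chance of a split.** Treat the two test statistics as bivariate normal with unit variance, correlation r and the same noncentrality, meaning the same standardised true effect on both measures. Then

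P(split) = p1 + p2 − 2·P(both significant).

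At 80% power each and r=0.74, P(both significant) = 0.719, so P(split) = 0.8 + 0.8 − 2×0.719 = 0.162.

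| True situation | Power, each measure | r=0.6 | r=0.74 | r=0.8 |
|---|---|---|---|---|
| No effect | 5% | 7.5% | 6.3% | 5.6% |
| 1.05 days | 23% | 22.0% | 17.7% | 15.5% |
| 1.7 days | 50% | 29.5% | 23.5% | 20.5% |
| 2.1 days | 68% | 26.2% | 20.9% | 18.3% |
| Stated design power | 80% | 20.2% | 16.2% | 14.2% |
| 3.0 days | 94% | 8.6% | 7.1% | 6.3% |

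Simulated two-sample t-tests with 81 per arm and a 2.4-day effect gave 17.0% (r=0.74) and 21.6% (r=0.6), close to the formula.

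**3. Direction.** P(self-report significant, PEth not) = (p1 − p2 + P(split))/2. At 80% power each this is 16.2/2 = 8.1% (r=0.74) and 20.2/2 = 10.1% (r=0.6).

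**4. Sensitivity to PEth power, which is an assumption.** At r=0.74, with self-report at 80%:

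| PEth power | P(split) | Self-report significant, PEth not |
|---|---|---|
| 70% | 20.1% | (10+20.1)/2 = 15.1% |
| 60% | 26.0% | (20+26.0)/2 = 23.0% |
| 50% | 33.3% | (30+33.3)/2 = 31.7% |

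**5. What a direct comparison could show.** Suppose half of a 2.4/5.5 = 0.436 SD self-report effect were reporting bias, so that the true gap is 0.218 SD. The SE of the difference in standardised effects is √(2/81)×√(2(1−r)), which is 0.141 at r=0.6 and 0.113 at r=0.74. The chance that a 95% CI excludes zero is Φ(0.218/SE − 1.96), or 34% and 49%.

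**The case against.** The strongest reply is that a split decides nothing by itself. It only starts a look at the scores, and PEth prevails only if their pattern fits under-reporting. The primary drinking-days analysis is still done, the rule sits under additional analyses, and the trial is a pilot. Most of this stands and limits the consequence. It does not rescue the trigger. The score criterion is not stated to be specific to an arm, and section 5.9.2 reports the social-desirability half of the pattern from earlier studies (0.88 points, p<0.01). If that recurs, the score step may not filter out splits caused by sampling error alone.

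A second reply is that self-report bias is a central measurement concern in section 3, so a check that triggers easily has value. This also stands. It is a reason not to close the score examination whenever the difference between the effects is unclear, because step 5 shows that the direct comparison would often miss a half-spurious effect.

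A reader might infer more than the documents support:

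- **A one-in-five rate.** The documents' own 80% power and 0.74 give about one in six. One in five needs a lower correlation or lower power, and neither figure describes the null or a large effect.
- **Every split is harmful.** At equal power, half have PEth significant, and concluding for PEth then keeps the true effect.
- **Nearly half of trials are affected.** At r=0.74, at least one split occurs in 46% of trials over the four active-versus-control comparisons. That counts both directions and assumes the full 2.4-day effect in both arms at both visits and a between-visit correlation of 0.6 that the documents do not give.
- **A third of comparisons split.** That needs PEth power near 50%, and the plan states none.

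**Conclusion.** The point holds in a limited form. The rule takes a difference in significance status for a difference in effect, and nothing else in the plan compares the effects. With a moderate true effect, shared equally by both measures, chance splits occur in about 16% of comparisons at the stated power and correlation, and in 14-30% over the plausible range. The direction that could lead to a true effect being called under-reporting accounts for 8-10% of comparisons at 80% power and r=0.6-0.74, and the conclusion changes only if the score pattern also fits.

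This rests on two-sided tests, comparable standardised effects, and a cross-sectional Spearman coefficient standing in for the correlation of the test statistics. Baseline adjustment and restriction to AUDIT-C-positive drinkers could lower that correlation, which would raise the split rate. Lower PEth power would raise both the split rate and the harmful share. The documents do not support saying that the rule by itself overturns the primary result.

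**What to change.** Replace the significance-based definition in section 5.9.2.

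- For each comparison, report the baseline-adjusted arm effects on drinking days and log10 PEth, each with a 95% CI.
- Add a bootstrap 95% CI, resampling participants, for the difference between the two effects on a common scale. Baseline-SD units are one choice. State the assumption that effects on a bounded count and on log10 PEth are comparable on that scale, since nothing in the documents establishes it.
- Do not label findings discordant, or conclude for PEth over self-report, on split p-values alone. Describe the measures as differing only when the CI for the difference supports it. Otherwise state that a difference was not shown, not that the results are consistent.
- Keep the social-desirability and demand examination in all cases, as a descriptive sensitivity analysis.

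The cost is SAP wording and a little more analysis on data already planned. The downside is limited power to demonstrate a true difference between the measures, as step 5 of the working shows. That is why the score examination should not depend on this interval.

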Valid measurement of unhealthy alcohol use is needed. In trials aiming to reduce certain behaviors, self-report of those behaviors can be especially problematic.⁸⁶⁻⁸⁸ For example, a recent alcohol pharmacotherapy trial showed declines in self-reported heavy drinking days in both the treatment and the control arms, while PEth declined only in the treatment arm.⁸⁹ The authors suggested that the control arm may have experienced an effect due to knowing that the intervention was to reduce alcohol (demand characteristics), and recommended using PEth in addition to self-report in future alcohol intervention trials.⁸⁹ PEth is a phospholipid which is formed only in the presence of alcohol and thus is highly specific.⁹⁰ PEth is the most sensitive medium-term biomarker,⁹¹ and PEth levels have been well correlated (Spearman's $r = 0.6-0.8$) with level of consumption in controlled studies.⁹²⁻⁹⁵ We found that PEth was 95% sensitive and 73% specific for detecting prior 21 day heavy drinking, and highly correlated with the number of drinking days in persons with HIV in Uganda⁹⁵ we have subsequently used PEth to confirm suspected under-reporting in that setting.^{96,97}

Table 1. Comparison of live versus automated phone-based counseling. Advantages highlighted and bolded.

	Live phone counseling	2-way SMS	2-way IVR
Importance of reading literacy	None	High	None
Importance of technical/phone literacy	Low	Medium	Low
Air time needed to respond to messages	No	Yes	No
Dependence on phone network quality	High	Low	Medium
Limits to length of message	None	160 chars	None
Ability to verify persons answering	High	Need PIN	Need PIN
Uniformity of messages*	Low	High	High
Ability to personalize (i.e. use names)	High	High	Low
Ability to tailor messages	High	Medium	Medium
Two-way capability	High	Medium	Medium
Messages remain on phone*	No	Yes	No
Capability for participant to communicate with the counselor	High	Medium, delayed	Medium, delayed
Flexibility in timing of boosters	Low	High	High
Flexibility in timing of attending to the message	Low	High	Medium: call back option
Anticipated cost per person	High	Low	Low

*May be an advantage or a disadvantage

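### The rule for settling discordant self-report and PEth results ignores study arm, so it can set aside a true self-report effect and cannot tell that case from misreporting that differs by arm

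*Combined protocol and SAP*

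**What the plan says.** Section 5.7.1 makes drinking days in the prior three weeks, by timeline follow-back, the primary outcome and uses PEth to confirm it. It justifies the choice partly because drinking days were "most highly correlated (Spearman $r=0.74$) with PEth level in a validation study in Uganda".

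Section 5.9.2 treats the two measures as agreeing, and the finding as conclusive, when "both analyses statistically significant or both not reaching statistical significance". If they disagree, the team looks at SDS and demand scores, and: "We will conclude in favor of the PEth results if the patterns are consistent with under-report". The pattern is spelled out as "associations of higher SDS and demand scores with lower self-reported alcohol use at the same PEth level, suggesting under-reporting". Neither the rule nor this explanation refers to study arm, and no test or threshold is given for deciding that the pattern is present.

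The same paragraph reports that in the team's earlier studies, with PEth held constant, "adjusted SDS means were 0.88 points lower ($p<0.01$) for those reporting versus those denying recent unhealthy alcohol use". It adds that SDS itself showed no relation to PEth (p = 0.28). Section 3.1 adds that self-report is known to under-estimate drinking in this population. Table 3 schedules SDS at baseline and 9 months, and the demand scale at 9 months only.

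**The concern.** The disagreement to be settled is about a difference between arms. Misreporting that is unrelated to arm leaves a difference in mean days essentially unbiased; misreporting that differs by arm does not. Section 3 gives an arm-related reason for using PEth: in an earlier drug trial, self-reported heavy drinking fell in both arms while PEth fell only in the treated arm, and a demand effect in the control arm was suspected. The rule in Section 5.9.2 does not carry that over. It asks whether people with higher scores report less at a given PEth level, which the team already expects for SDS.

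The demand score raises a second problem. It is taken after the intervention. Counselled participants may be more aware of the hypothesis and, if counselling works, drink less. Since PEth tracks drinking imperfectly, an association that ignores arm can then appear with no misreporting at all.

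At stake is which efficacy result is believed for the primary outcome whenever the two measures disagree.

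**Working it through.** **Inputs from the documents.** 90 per arm with 90% retention, so 81 evaluable; SD 5.5; difference 2.4 days; alpha 0.05, taken as two-sided (Section 5.9.1). Correlation of self-reported days with PEth 0.74 (Section 5.7.1). SDS gap 0.88 points (Section 5.9.2).

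**Assumptions, not in the documents.** SDS SD of 2 to 3; 30 to 50% of participants denying unhealthy use; misreporting that rises with SDS equally in both arms; SDS independent of arm and of PEth; normal outcomes analysed by least squares without a baseline covariate.

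**Step 1: the plan's own figure.** Standard error = 5.5 × √(2/81) = 0.864. Then 2.4/0.864 = 2.78, and 2.78 − 1.96 = 0.82, giving power of 79.3% (78.8% by t-test) against the stated 80%. It reproduces.

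**Step 2: strength of the SDS pattern.** With d = 0.88/SD and q the share denying, r = d/√(d² + 1/(q(1−q))).
- SD 2, q = 0.5: 0.44/√(0.194 + 4) = 0.215.
- SD 3, q = 0.3: 0.293/√(0.086 + 4.762) = 0.133.

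The range is about 0.13 to 0.22.

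**Step 3: true 2.4-day effect, equal misreporting.** 10,000 simulated two-arm trials per row. Self-report is significant in about 79% and PEth in about 54%. The pattern is the SDS coefficient in a regression of self-report on PEth and SDS.

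| Partial r | Self-report only significant | Pattern significant, given that | Pattern has the sign, given that | Overturned (significance) | Overturned (sign) |
|---|---|---|---|---|---|
| 0.12 | 27.5% | 30.5% | 92.7% | 0.275 × 0.305 = 8% | 25% |
| 0.17 | 26.3% | 57.5% | 98.6% | 0.263 × 0.575 = 15% | 26% |
| 0.21 | 26.0% | 74.8% | 99.6% | 0.260 × 0.748 = 19% | 26% |

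At r = 0.215 a normal approximation gives 78% significant, so 0.26 × 0.78 = 20%. With no SDS-related misreporting at all, self-report alone is still significant in 28%, because PEth has less power. At correlations of 0.6 and 0.8 (r = 0.17) that share is 42% and 20%, and the pattern is again significant in about 57% of those trials.

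**Step 4: can the rule separate the two cases?** Now let there be no true effect and let all 2.4 days be misreporting in one arm. At r = 0.17 the pattern is significant in 53% of self-report-only trials, against 57% under the true effect. With an SDS slope of 0.65 day per SD (0.65/5.5/√(1 − 0.74²) = 0.18 as a partial r), the figures are 57% and 59%. If misreporting is unrelated to SDS, the pattern is significant in 2.6%, so arm-differential bias is missed.

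**Step 5: demand score.** With a real effect, no misreporting, and counselled participants scoring 0.5 to 1 SD higher (assumed), the demand coefficient has the required sign in about 72 to 88% of self-report-only trials (50% by chance) and is significant in about 8 to 18% (about 2% by chance).

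**Step 6: why a by-arm check needs care.** If PEth correlates 0.74 with days, a true 2.4-day effect leaves an arm gap at a given PEth level of 2.4 × (1 − 0.74²) = 1.1 days with no misreporting. In the simulations of Step 3 that raw gap was significant in about 66 to 69% of self-report-only trials.

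**The case against.** The strongest reply is that preferring an objective biomarker where under-reporting is documented is a defensible choice made in advance. The trial is a pilot meant to supply effect sizes, the rule sits under additional analyses, and nothing suppresses the self-report estimate. That limits the damage, but the rule still says which result to believe for the primary outcome.

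Several specific points stand:
- The Section 3 example is the reverse discordance, with PEth showing an effect and self-report not. Siding with PEth is right there. That case is rare under equal misreporting (2 to 3% of simulated trials) but matters if controls under-report.
- The rule names SDS and demand scores together. If both must show the pattern it fires less often, so the SDS-only figures are upper bounds.
- The 0.74 relates PEth to self-reported, not true, days, and the simulation omits the planned count model and baseline adjustment.
- Equal misreporting is not wholly harmless on the planned log scale: taking 1 day from means of 7 and 4.6 moves the rate ratio from 4.6/7 = 0.66 to 3.6/6 = 0.60.
- The team may intend to look by arm. Nothing written says so.

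A reader might also infer that an arm-by-SDS interaction is the natural replacement. It is not. It tests whether the SDS slope differs by arm, not whether misreporting does. When the counselled arm under-reports by a flat 2.4 days it fires in only about 3% of self-report-only trials. When flat under-reporting by controls masks a true effect, it backs PEth in about 2 to 3% of PEth-only trials, against about 60% for the present rule.

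**Conclusion.** The concern holds in a limited form. As written, the rule can set aside a true self-report effect, and it cannot distinguish that case from misreporting that differs by arm. With 81 per arm, SD 5.5, a 2.4-day effect, a correlation of 0.74, equal misreporting and a partial r of about 0.12 to 0.22, roughly 8 to 20% of true-effect trials could be overturned if the pattern must be significant, or about 25% if its sign suffices. These figures rest on an assumed SDS SD and share of deniers, on least squares without baseline, and on the SDS part alone.

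A reader might go further and say that the rule would overturn true effects as a matter of course, or that its trigger is a foregone conclusion. The documents do not support that. It matters only when the measures disagree, no threshold is stated, the result from the team's previous studies covers SDS and not demand scores, and significance is far from certain (about 31 to 78% of self-report-only trials). Nor can one say that equal misreporting could never produce disagreement, given the log-scale shift above.

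**What to change.** Reword the discordance paragraph in Section 5.9.2 before analysis:
- The association of SDS and demand scores with self-report, taken without regard to arm, does not decide a discordant comparison.
- For each discordant comparison, report the self-report and PEth arm estimates with confidence intervals.
- Examine by arm whether self-report relative to PEth differs: self-report minus PEth-predicted use, by arm, with an interval and an allowance for PEth being an imperfect proxy (for example, over correlations of 0.6 to 0.8, the range cited in Section 3). Show SDS and demand associations within arm as supporting description.
- Apply this in both directions of discordance, including under-reporting in the control arm.
- Attribute the discordance to misreporting only if there is evidence that it differs by arm in the direction that explains it. Otherwise call the comparison unresolved.
- Do not use the arm-by-SDS interaction alone as the criterion.
- State what will be done at 6 months, when Table 3 schedules neither SDS nor the demand scale.

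The cost is SAP wording and a modest extra analysis of data already being collected. The downside is that more discordant comparisons will be reported as unresolved.
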